**Duration of Treatment:**

The double-blind treatment phase 6 weeks

The open-label treatment phase 28 weeks (outside Japan) or 52 weeks (in Japan)

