**Table 4 Schedule of Assessments for outside Japan (Open-label treatment phase)**

	Double-blind treatment phase	Open-label treatment phase (28 weeks)									Discontinuation	Follow-up phase (1-2 weeks)
Visit No.	6	101	102	103	104	105	106	107	108	109	Discontinuation visit	Follow-up visit
Timeline from the beginning of the open-label treatment phase a (Study timeline)	- (Week 6)	Open-Week 1 (Week 7)	Open-Week 2 (Week 8)	Open-Week 4 (Week 10)	Open-Week 8 (Week 14)	Open-Week 12 (Week 18)	Open-Week 16 (Week 22)	Open-Week 20 (Week 26)	Open-Week 24 (Week 30)	Open-Week 28 (Week 34)	-	-
Visit window in the open-label treatment phase (Day)	-	Open-5-11	Open-12-18	Open-26-32	Open-50-64	Open-78-92	Open-106-120	Open-134-148	Open-162-176	Open-190-204	At discontinuation +5 f	6-17 days after completion of treatment or discontinuation e
Hospitalization b	←-----											
Inclusion/ Exclusion criteria assessments	(X)											
Dispense study drug	(X)	X	X	X	X	X	X	X	X	X		
Study treatment compliance	(X)	X	X	X	X	X	X	X	X	X	X	
PANSS	(X)	X	X	X	X	X	X	X	X	X e	X e	
CGI-S	(X)	X	X	X	X	X	X	X	X	X e	X e	
DIEPSS	(X)	X	X	X	X	X	X	X	X	X e	X e	
C-SSRS	(X)	X	X	X	X	X	X	X	X	X e	X e	
Skin irritation assessment	(X)	X	X	X	X	X	X	X	X	X	X	
Laboratory test c	(X)			X		X		X		X e	X e	
Pregnancy test d	(X)									X	X	
12-lead ECG	(X)			X		X		X		X e	X e	
Body weight	(X)	X	X	X	X	X	X	X	X	X	X	
Body temperature, blood pressure, pulse rate	(X)	X	X	X	X	X	X	X	X	X	X	
Adverse event monitoring	←-----											
Blood sampling for PK	(X)									X e	X e	

- a Open-Day 1 is defined as the day of the initial application of the study drug in the open-label treatment phase.
- b All subjects can be inpatients or outpatients.
- c At Visit 109 and at the discontinuation visit, blood samples will be collected under fasting conditions (at least 10 hours after the last meal). At other visits, blood samples should be collected under fasting conditions (at least 10 hours after the last meal) whenever possible.
- d To be performed only in female subjects who are premenopausal and of childbearing potential.
- e Must be performed before the beginning of post-treatment with antipsychotics excluding the study drug.

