**Table 5 Schedule of Assessments for Japan (Open-label treatment phase)**

	Double-blind treatment phase	Open-label treatment phase (52 weeks)												Discontinuation	Follow-up phase (1-2 weeks)
Visit No.	6	101	102	103	104	105	106	107	108	109	110	111	112	Discontinuation visit	Follow-up visit
Timeline from the beginning of the open-label treatment phase a (Study timeline)	- (Week 6)	Open-Week 1 (Week 7)	Open-Week 2 (Week 8)	Open-Week 4 (Week 10)	Open-Week 8 (Week 14)	Open-Week 12 (Week 18)	Open-Week 16 (Week 22)	Open-Week 20 (Week 26)	Open-Week 24 (Week 30)	Open-Week 28 (Week 34)	Open-Week 36 (Week 42)	Open-Week 44 (Week 50)	Open-Week 52 (Week 58)	-	-
Visit window in the open-label treatment phase (Day)	-	Open-5-11	Open-12-18	Open-26-32	Open-50-64	Open-78-92	Open-106-120	Open-134-148	Open-162-176	Open-190-204	Open-239-267	Open-295-323	Open-351-379	At discontinuation +5 f	6-17 days after completion of treatment or discontinuation e
Hospitalization b	←----->														
Inclusion/ Exclusion criteria assessments	(X)														
Dispense study drug	(X)	X	X	X	X	X	X	X	X	X	X	X	X		
Study treatment compliance	(X)	X	X	X	X	X	X	X	X	X	X	X	X	X	
PANSS	(X)	X	X	X	X	X	X	X	X	X	X	X	X e	X e	
CGI-S	(X)	X	X	X	X	X	X	X	X	X	X	X	X e	X e	
DIEPSS	(X)	X	X	X	X	X	X	X	X	X	X	X	X e	X e	
C-SSRS	(X)	X	X	X	X	X	X	X	X	X	X	X	X e	X e	
Skin irritation assessment	(X)	X	X	X	X	X	X	X	X	X	X	X	X	X	
Laboratory test c	(X)			X		X		X		X	X	X	X e	X e	
Pregnancy test d	(X)												X	X	
12-lead ECG	(X)			X		X		X		X	X	X	X e	X e	
Body weight	(X)	X	X	X	X	X	X	X	X	X	X	X	X	X	
Body temperature, blood pressure, pulse rate	(X)	X	X	X	X	X	X	X	X	X	X	X	X	X	
Adverse event monitoring	←----->														
Blood sampling for PK	(X)									X			X e	X e	

- a Open-Day 1 is defined as the day of the initial application of the study drug in the open-label treatment phase.
- b All subjects can be inpatients or outpatients
- c At Visit 112 and at the discontinuation visit, blood samples will be collected under fasting conditions (at least 10 hours after the last meal). At other visits, Blood samples should be collected under fasting conditions (at least 10 hours after the last meal) whenever possible.
- d To be performed only in female subjects who are premenopausal and of childbearing potential.

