2.2 Overall Study Design

This study has two main phases:

1. Double-blind treatment phase: Multicenter, randomized, double-blind, placebo-controlled, parallel-group design
2. Open-label treatment phase: Multicenter, open-label, flexible dose design

The flowchart for this study is given in Figure 1.

Figure 1: Study Flowchart

The study consists of 4 phases: the washout phase, the double-blind treatment phase, the Open-label treatment phase, and the follow-up phase.

In the washout phase, placebo will be applied once daily for 1 week (at least 3 days) in a single-blind manner. After the washout phase, subjects will be randomized to one of three treatments: 40 mg of DSP-5423P, 80 mg of DSP-5423P, and placebo, at 1:1:1 ratio in the Double-blind treatment phase. The study drugs will be applied once daily for 6 weeks. Subjects who completed the double-blind treatment phase can enter the Open-label treatment phase. In the open-label treatment phase, DSP-5423P will be applied as flexible dose (40, 60, or 80 mg) once daily for 28 weeks (outside Japan) or 52 weeks (in Japan).

Subjects who completed the open-label treatment phase or who prematurely discontinued the study drug after entering the double-blind treatment phase will undergo the follow-up assessments in 1 to 2 weeks after the termination of the study drug.

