7.7.1 Adverse Events

Treatment emergent AEs (TEAEs) are defined as follows:

- TEAEs (the double-blind treatment phase): Events with start date on or after the date of initial application of study drug in the double-blind treatment phase, and up to 17 days after the date of final application of study drug in the double-blind treatment phase and before the first application of DSP-5423P in the open-label treatment phase.
- TEAEs (DSP-5423P treatment period): Events with start date on or after the date of initial application of DSP-5423P either in the double-blind treatment period for 40MG and 80MG groups or in the open-label treatment period for placebo group and up to 17 days after the date of final application date of DSP-5423P.

AE with missing or incomplete start date after imputation will be considered as TEAE.

Treatment-related TEAE:

A treatment-related TEAE is defined as a TEAE for which the causal relationship to the study treatment is either 'definite', 'probable', or 'possible'.

Common TEAE:

Common TEAE in the double-blind treatment phase are PT of TEAEs experienced by 2% or more subjects in 40MG or 80MG group in the safety population.

Common TEAE in the DSP-5423P treatment period are PT of TEAEs experienced by 2% or more subjects in the overall-to-FLEX DOSE group in the DSP-5423P dosed population.

The summary of AEs will be limited to treatment-emergent AEs (TEAEs). The number and percentage of subjects with TEAEs during the double-blind treatment phase on the safety population and DSP-5423P treatment period on the DSP-5423P dosed population will be summarized by preferred term, system organ class, and treatment group. Summaries will be repeated by country and race.

Specifically, this will cover the following items:

- any TEAE;
- TEAE leading to death;
- TEAE leading to treatment discontinuation;
- serious TEAE;

- extrapyramidal TEAE;
- skin-related TEAE;
- treatment-related TEAE;
- treatment-related TEAE leading to death;
- treatment-related TEAE leading to treatment discontinuation;
- treatment-related serious TEAE;
- treatment-related extrapyramidal TEAE;
- treatment-related skin-related TEAE;

Skin-related TEAE is defined as the TEAE occurred at the application site (recoded in the CRF) and identified as TEAE with a wording “Application site” in MedDRA LLT.

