For the summaries by DSP-5423P dose at onset, if a subject experienced more than one episode of an TEAE within a PT, the subject is counted only once in the PT by DSP-5423P dose at onset. For example, if a subject has same PT twice but onset dose for each is not same, these PTs will appear one time each in different dose categories. Denominator of percentage for each dose is the number of subjects who have experienced the dose of interest at least once in the DSP-5423P treatment period in case that no DSP-5423P dose at onset is available, for example, the onset date is middle of prescribed periods or the onset date is after the final application, DSP-5423P dose at onset will be set to last non-missing dose taken at prior to the onset date.

No statistical comparisons of AEs between treatment groups will be performed.

Narrative of Serious AE will be produced by a subject who experienced SAE.

Hospitalization record will be listed.

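### Final DSP-5423P-period adverse-event tables use crude percentages despite 28 versus 52 open-label weeks and unequal time on each dose, so country and dose-at-onset figures are not comparable

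*SAP*

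**What the plan says.** **Start of counting.** Under SAP 7.7.1, DSP-5423P-period TEAEs count from first application of active drug, "either in the double-blind treatment period for 40MG and 80MG groups or in the open-label treatment period for placebo group". Counting stops 17 days past the last application.

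**Planned length.** Protocol synopsis (Duration of Treatment) and SAP 2.2 give 6 double-blind weeks, then 28 open-label weeks outside Japan or 52 in Japan.

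**Metric.** SAP 7.7.1 gives the number and percentage of subjects. The overview and the main table are repeated by country and race; the common, extrapyramidal and skin-related tables are repeated by country. SAP 7.7.8 also lists country as a TEAE subgroup. A preferred term is common in this period if "experienced by 2% or more subjects in the overall-to-FLEX DOSE group in the DSP-5423P dosed population".

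**Dose at onset.** For this table, "Denominator of percentage for each dose is the number of subjects who have experienced the dose of interest at least once".

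**Related provisions.**
- TEAEs are also tabulated by first-onset interval, with treated subjects as the denominator of each interval. That table carries no mark for repetition by country.
- SAP 7.5.1 summarises exposure duration by group and country but does not link it to event counts.
- SAP 7.9 limits the submission summary to events before Open Day 177. The final analysis includes all data.

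Neither document plans a person-time rate, a Kaplan-Meier estimate for adverse events, or a common horizon for the final analysis.

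**The concern.** Long-term safety is a stated secondary objective (Protocol 5.2, SAP 2.1). A crude percentage depends on how long subjects are watched. The final by-country tables place subjects planned for 52 open-label weeks beside subjects planned for 28, so Japan can show higher percentages when the underlying rate is the same everywhere. The 2% threshold for common events is applied to a pool that mixes these horizons.

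The dose-at-onset table has the same weakness in sharper form. Everyone who enters the open-label phase spends time at 40 mg, and anyone who reaches 80 mg there passes through 60 mg. A short stay puts a whole subject into the denominator of the lower dose. A reader could take the resulting pattern for a dose-response. The open-label phase has no concurrent placebo group against which to check either reading.

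**Working it through.** **Planned exposure.** Placebo-first: 28 or 52 weeks. Active-first: 6 + 28 = 34 or 6 + 52 = 58 weeks. The last two reproduce the Week 34 and Week 58 labels of the final open-label visits in Protocol Tables 4 and 5. From SAP Appendix II, Japan contributes 25 + 28 + 42 + 29 + 24 + 16 = 164 of 582 randomized subjects (28.2%); the 42 covers sites 117 to 126.

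The documents give no event rates, hazard shapes or open-label dropout. Those below are assumptions, shown as a range.

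**Country, placebo-first subjects, same hazard everywhere.** Fix the risk at 10% by 28 weeks: h = -ln(0.9)/28 = 0.003763 per week.

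- Full completion, constant hazard: 1 - exp(-52h) = 17.8%. With the 17-day tail added to both horizons, and 10% still set for the shorter, the longer one gives 17.2%.
- Exponential open-label dropout at rate L, with L = -ln(1 - dropout by Week 28)/28. Crude incidence at W weeks = h/(h+L) × [1 - exp(-(h+L)W)].
- Hazard decaying as exp(-t/τ), scaled to 10% at 28 weeks: risk at 52 weeks = 1 - 0.9^k, with k = [1 - exp(-52/τ)]/[1 - exp(-28/τ)].

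| Assumption | 28 weeks | 52 weeks |
|---|---|---|
| Constant hazard, full completion | 10.0% | 17.8% |
| Constant hazard, 30% dropout by Week 28 | 8.4% | 13.1% |
| Constant hazard, 50% dropout by Week 28 | 7.3% | 10.2% |
| τ = 16 weeks, full completion | 10.0% | 11.5% |
| τ = 8 weeks, full completion | 10.0% | 10.3% |
| τ = 4 weeks, full completion | 10.0% | 10.0% |

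At the threshold for common events, 2.0% at 28 weeks becomes 3.7% at 52 weeks (constant hazard, full completion). In the constant-hazard cases the rate is the same in both regions: 100 × 0.003763 × 52.18 = 19.6 first events per 100 person-years.

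**Dose at onset.** Protocol 10.1.3 sets 40 mg from Visit 6 to Visit 101 (Open-Week 1). Protocol 10.2 allows 20 mg steps, in principle at least a week apart. The fastest scheduled titration for a placebo-first subject outside Japan is therefore about 1 week at 40 mg, 1 at 60 mg and 26 at 80 mg. Assume 0.5 events per person-year at every dose; the chance of at least one event on a dose held for T weeks is 1 - exp(-0.5T/52.18).

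- 40 mg, T = 1: 1.0%
- 60 mg, T = 1: 1.0%
- 80 mg, T = 26: 22.1%; in Japan, T = 50: 38.1%

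Double-blind time alters the mix. On the same titration, a 40 mg-first subject has 6 + 1 = 7 weeks at 40 mg (6.5%), and an 80 mg-first subject outside Japan has 6 + 26 = 32 weeks at 80 mg (26.4%). The pooled table would average over such subjects and over slower titrations.

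**Prior arm.** The dosed population includes active-arm subjects who drop out during the double-blind phase, but placebo-arm subjects only if they complete it and enter open-label treatment (SAP 5.5; Protocol 8.3.1). The sample-size inflation implies dropout of 1 - 133/167 = 20.4%. Assume dropout is uniform over 6 weeks (mean 3 weeks) with none in the open-label phase:

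- Outside Japan: 0.796 × 34 + 0.204 × 3 = 27.7 weeks active-first, against 28.0 placebo-first.
- Japan: 0.796 × 58 + 0.204 × 3 = 46.8 against 52.
- At an assumed 10% dropout: 30.9 against 28 outside Japan, and 52.5 against 52 in Japan.

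**The case against.** The strongest reply is that these tables are descriptive and the plan already limits the harm. SAP 7.7.1 rules out statistical comparison of adverse events between groups, and exposure duration is shown by country. The submission summary drops events from Open Day 177 in every country, so Japan and the other countries share one open-label horizon there. The first-onset table counts from first active application and is shown by prior arm; its windows up to Week 26 lie inside all four planned durations. All of this stands. It confines the country problem to the final analysis and largely answers the prior-arm comparison. It does not cover country in the final tables, because the onset table is not marked for that repetition. Its first two windows, Weeks 1 to 6 and Weeks 1 to 13, also overlap.

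A second reply is that dose was adjusted on response and adverse events, so person-time by dose still yields no causal dose comparison. That is true and should be stated on the table. It is no reason to keep a denominator that also ignores time on dose.

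Two stronger readings are tempting. A reader might infer that active-first subjects will look worse than placebo-first subjects because their planned maximum is 6 weeks longer. The documents do not support a fixed direction: one group includes double-blind dropouts, the other only completers, and at the implied dropout mean exposure is about equal or reversed. A reader might also infer a spurious gap between Japan and elsewhere of 9 to 22 percentage points. That needs 0.25 to 1.0 events per person-year, constant hazard and no dropout, so it is a ceiling for those rates.

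**Conclusion.** The point holds for the final analysis. By-country TEAE percentages are not comparable, because planned open-label time is 28 weeks outside Japan and 52 weeks in Japan and no time denominator or common horizon is set. For an event at 10% by 28 weeks, the artefact ranges from 7.8 points (constant hazard, full completion) through 4.7 and 2.9 points (30% and 50% open-label dropout) to 1.5 points or none (strongly early events). It would therefore be wrong to say that country differences must mainly reflect time at risk.

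The dose-at-onset denominator can create an apparent dose trend at equal rates: about 1%, 1% and 22% in the illustration, which rests on the fastest scheduled titration and an assumed rate. Prior-arm groups are not directly comparable either, but the direction is not fixed.

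The country imbalance does not reach the submission summary. No hypothesis test, decision rule or primary result is affected. This is an inexpensive improvement to the reporting of a secondary objective.

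**What to change.** Keep the crude tables and add the following to SAP 7.7.1 for the DSP-5423P treatment period:

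- (a) Subjects with a first event per 100 person-years at risk, with confidence interval, for any, serious, extrapyramidal, skin-related and common TEAEs, overall and by country.
- (b) In the dose-at-onset table, person-time on each dose as the denominator, with a note that the table is descriptive because dose was adjusted on response and adverse events.
- (c) For the final by-country tables, either a version limited to events through open-label Week 28, or the first-onset table repeated by country with its overlapping first two windows corrected.

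The onset, application and prescription dates needed are already used in the SAP. The cost is a few extra columns and the constant-rate simplification behind (a), which (c) offsets by comparing like windows without it. Person-year rates will not remove the selection difference between prior arms; a footnote should say so.

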### **6.3 Safety Endpoints**

- Adverse events (AEs) and adverse drug reactions (ADRs)
- Extrapyramidal AEs and ADRs
- Skin-related AEs and ADRs at the application site
- Assessment of skin irritation reaction at the application site
- Change in Drug-Induced Extrapyramidal Symptoms Scale (DIEPSS) total score (excluding overall severity) from baseline at Week 6
- Change in individual DIEPSS scores from baseline at Week 6
- Change in DIEPSS total score (excluding overall severity) from the last evaluation before the initial application of DSP-5423P at each visit
- Change in individual DIEPSS scores (excluding overall severity) from the last evaluation before the initial application of DSP-5423P at each visit
- Serum prolactin concentration
- Electrocardiogram (ECG) parameters (QTc)
- Concomitant use of antiparkinson drugs
- Assessment of suicide using Columbia-Suicide Severity Rating Scale (C-SSRS)
- Laboratory test values, vital signs, and body weight

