## **12.3 Collection and Recording Adverse Events**

All AEs will be, in principle, followed up until resolution, stabilization of the condition, the event is otherwise explained, or the subject is lost to follow-up. All AEs must be collected and recorded in the subject's study records/source documents, in accordance with the Investigator's normal clinical practice. AEs will be recorded in the CRFs

from the beginning of the study treatment in the washout phase until the follow-up visit.

Each AE is to be evaluated for duration, severity, seriousness, action taken with the study treatment, outcome, and causal relationship to the study treatment. If any AEs related to skin disorders occur at the application site, the Investigator will record the location (the back, chest or abdomen) of AEs occurrence.

Definitions for severity, action taken with the study treatment, outcome, and causal relationship to the study treatment are presented below.

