### **15.3.6 Safety Analysis**

#### **15.3.6.1 Adverse Events**

The summary of AEs will be limited to treatment-emergent AEs (TEAEs), which are defined as AEs with onset on or after Day 1. An ADR will be defined as an AE related to the study treatment; an AE of which causality with study drug is related, probably related, or possibly related.

The number and percentage of subjects with at least one AE or ADR in the double-blind treatment phase for each preferred term and system organ class will be summarized by treatment group. Also, the number and percentage of subjects with at least one AE or ADR developing after applying DSP-5423P during the entire study duration will be summarized overall and by treatment group. This summary will be repeated for death, SAEs, AEs leading to study discontinuation, severe AEs, extrapyramidal AEs, and skin-related AEs at the application site.

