The number and percentage of subjects reporting each TEAE will be summarized by system organ class (SOC) and preferred term (PT) for the double-blind treatment phase on the safety population and for the DSP-5423P treatment period on the DSP-5423P dosed population. Whenever appropriate, SOCs are sorted by alphabetically and PTs are sorted within SOC in descending order of frequency of the active group for the double-blind treatment phase and the Overall-to-FLEX DOSE group for the DSP-5423P treatment period. If there are ties, PTs are sorted by alphabetically. The following summaries will be produced for the double-blind treatment phase and DSP-5423P treatment period:

- TEAE by SOC and PT*;
- Common TEAE by PT#;
- treatment-related TEAE by SOC and PT;
- TEAE by maximum severity and PT;
 - This will be repeated for extrapyramidal TEAE and skin related TEAE
- TEAE leading to treatment discontinuation by SOC and PT+;
- Serious TEAE by SOC and PT;
- extrapyramidal TEAE by PT#+;
- skin related TEAE by PT#+;
- skin related TEAE by PT and application site;

Statistical Analysis Plan

Version: 2

Study No. D4904020

- TEAEs by first onset (Day 1 to 7, Day 8 to 14, Day 15 to 28, Day 29 or later), SOC and PT in the double-blind treatment phase;
 - This will be repeated for extrapyramidal TEAE and skin related TEAE
 - TEAEs by first onset (Week 1 to 6, 1 to 13, 14 to 26, 27 to 39, 40 to 52, 53 or later, Week 1=Day 1 to 7, Week 2=Day 8 to 14), SOC and PT in the DSP-5423P treatment period;
 - This will be repeated for extrapyramidal TEAE and skin related TEAE
 - TEAEs by DSP-5423P dose at onset (40MG, 60MG, 80MG), SOC and PT in the DSP-5423P treatment period;
 - TEAEs by modal daily dose (40MG, 60MG, 80MG), SOC and PT in the DSP-5423P treatment period;
 - TEAEs leading to dose reduced by SOC and PT in the DSP-5423P treatment period+;
 - TEAEs leading to dose increased by SOC and PT in the DSP-5423P treatment period+;
- * Summaries will be repeated by country and race. # Summaries will be repeated by country. +: listing will be produced.

In the above summaries, unless otherwise specified, if a subject experienced more than one episode of a TEAE within a PT or a SOC, the subject is counted only once in the PT or the SOC.

For summaries based on DSP-5423P treatment period and on-going event carried from DB phase, the following items will be handled as described. No handling will be applied for items not listed below;

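### SAP 7.7.1 adds a MedDRA term condition to skin-related TEAEs that the protocol endpoint lacks, so a located skin event coded to a general term drops out of the dedicated skin summaries (minor)

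*SAP*

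**What the plan says.** Protocol 6.3 names the safety endpoint as "Skin-related AEs and ADRs at the application site". Protocol 15.3.6.1 carries the same idea into the analysis, where the AE summary is repeated for "extrapyramidal AEs, and skin-related AEs at the application site". Neither section sets a dictionary-term condition.

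The site is captured directly. Protocol 12.3 states: "If any AEs related to skin disorders occur at the application site, the Investigator will record the location", the choices being back, chest or abdomen.

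SAP 7.7.1 defines the category as follows: "Skin-related TEAE is defined as the TEAE occurred at the application site (recoded in the CRF) and identified as TEAE with a wording". The sentence ends by naming the wording to look for: "identified as TEAE with a wording “Application site” in MedDRA LLT". The two conditions are joined by 'and'.

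The definition feeds these outputs in SAP 7.7.1:
- the overall counts of skin-related and treatment-related skin-related TEAEs;
- the table by preferred term, repeated by country and accompanied by a listing;
- the table of "skin related TEAE by PT and application site";
- the tables by maximum severity and by first onset.

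SAP section 8 records no change from the planned analyses.

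**The concern.** Local skin tolerability is a named safety endpoint of a transdermal product. The SAP category is narrower than that endpoint, because it requires a text match on the coded term as well as the site.

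A mismatch between the two sources is foreseeable. The CRF holds location in its own field, so the reported term need not repeat it. Protocol 12.1.1 and 12.2 ask for a diagnosis in place of individual signs where one is available. A diagnosis such as contact dermatitis carries no site in its wording. An event of this kind could have its site recorded and still be coded to an LLT without the words 'Application site'. It would then be missing from all the dedicated skin outputs, including the skin-related listing. The general tables would hold it, but no planned table there marks it as an application-site event.

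**Working it through.** The documents give no rate, count or coding split for skin-related TEAEs, so there is no figure to reproduce. The check is one of logic.

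**Inputs.** A: the CRF places the event at the application site (protocol 12.3; first condition in SAP 7.7.1). B: the LLT contains 'Application site' (second condition in SAP 7.7.1). The word 'recoded' in the SAP sentence is read as a typing error for 'recorded'.

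| A (CRF site) | B (LLT) | A and B: SAP as written | B only: LLT as identifier | A only: protocol endpoint | A or B |
|---|---|---|---|---|---|
| yes | yes | counted | counted | counted | counted |
| yes | no | **not counted** | **not counted** | counted | counted |
| no | yes | not counted | counted | not counted | counted |
| no | no | not counted | not counted | not counted | not counted |

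**Second row.** This is the case at issue. The event is lost whether the SAP sentence means both conditions, or means that the LLT wording is simply how the programmer finds application-site events. Only a rule that lets the CRF site record suffice keeps it.

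**Third row.** The written rule also loses an event with an 'Application site' LLT and no site in the CRF.

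**Direction.** Every event meeting A and B also meets A. The SAP count can therefore equal the protocol's count or fall below it, but cannot exceed it.

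**Size.** Let p be the true share of subjects with a located skin event. Let f be the share of those subjects whose events are all coded to general terms. Then:

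reported incidence = p × (1 − f)

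As an illustration on assumed numbers only, take 20 affected subjects in an arm of the planned 167, so p = 20/167 = 12.0%.

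- f = 0: 20 × 1.00 = 20 subjects, 20/167 = 12.0%
- f = 10%: 20 × 0.90 = 18 subjects, 18/167 = 10.8%
- f = 25%: 20 × 0.75 = 15 subjects, 15/167 = 9.0%

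The 20 subjects and the values of f come from neither document.

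**The case against.** The strongest reply is that the two conditions may coincide in practice. Protocol 12.3 asks for a location specifically for skin events at the application site. If coders use that field when they choose the LLT, every located event receives an 'Application site' term and f is zero. The SAP cites the eCRF but it is not among the documents reviewed, and no coding convention is given. If 'recoded' were meant literally, as recoding located events to application-site terms, the gap would also close. These points stand as possibilities. Neither document describes such a step, and the SAP does not require one.

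The consequence is also limited. SAP 7.7.1 plans no statistical comparison of AEs between groups. Investigators and assessors are blinded in the double-blind phase, so nothing in the documents suggests that reported wording would differ by arm. Investigator-scored skin irritation is a separate endpoint, independent of MedDRA coding (protocol 11.3.4; SAP 7.7.4). This stands, and it is why the point is minor. The irritation scores do not replace the AE summaries, however, because they carry no causality, seriousness or discontinuation data.

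A reader might go further in three ways that the documents do not support:
- **That the events vanish from the report.** They do not. SAP 7.7.1 keeps them in the general tables by system organ class and preferred term, and safety data are listed.
- **That a few such records could move a term across the 2% threshold for common TEAEs.** They could not. That table counts preferred terms over all TEAEs and does not use the skin-related definition.
- **That wording differences across the eight countries in SAP Appendix II distort the by-country skin table.** Protocol 16.1 requires CRF data in English. Wording may still vary, but nothing shows that it does.

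**Conclusion.** The point holds as a gap in definition. The SAP category is narrower than the protocol's site-based endpoint. A skin event located at the application site but coded to a general LLT would be left out of all dedicated skin-related TEAE summaries, under either reading of the SAP sentence.

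An actual undercount is not established. Its size depends on f, which the documents do not give and which may be zero. The conclusion rests on reading 'recoded' as 'recorded', and on there being no unstated convention that ties the LLT to the CRF location. The effect is confined to descriptive safety outputs. The primary analysis, type I error and power are untouched. The severity is minor.

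**What to change.** In SAP 7.7.1, define a skin-related TEAE by the CRF application-site record, which matches the protocol. Alternatively, define it by either that record or an LLT containing 'Application site'. The first option is the closer match. The second also recovers application-site terms whose location was left blank. Correct 'recoded' if 'recorded' was meant.

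Under either option, list the records that meet only one condition and resolve them at the blinded data review already planned before unblinding of the double-blind phase. Treat open-label records in the same way before the data locks that follow. Show any event still lacking a location as 'not specified' in the table by preferred term and application site.

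The cost is a one-line change, one extra listing and a reported incidence that may be slightly higher. If coding already follows location and no site record is missing, the results do not change.
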